1.5 Dose Rationale and Risk/Benefits

The recommended dose of Anakinra for the treatment of patients with rheumatoid arthritis is 100 mg/day administered daily by subcutaneous injection. Higher doses did not result in a higher response. As such, the same dosing recommendations will be used for patients with Autoimmune Inner Ear Disease. The dose should be administered at approximately the same time every day. In order to determine efficacy, hearing thresholds will be monitored by audiogram every 28 days during the 84-day trial period. In a single case study of a patient with Muckle-Wells syndrome, a three month treatment regimen of 100mg/day resulted in restoration of normal hearing to a patient with bilateral sensorineural hearing loss (PTA prior to treatment: AS: 46dB AD: 43dB, PTA post treatment AS: 11dB AD: 9dB) (**17**).

Instructions on appropriate use should be given by the healthcare provider to the patient or caregiver. Patients or caregivers should not be allowed to administer Anakinra until the patient or

CONFIDENTIAL This material is the property of the Feinstein Institute for Medical Research, North-Shore-LIJ Health System. Do not disclose or use except as authorized in writing by the study sponsor caregiver has demonstrated a thorough understanding of procedures and an ability to inject the product. After administration of Anakinra, it is essential to follow the proper procedure for disposal of syringes and needles. See the "Patient Information" insert for detailed instructions on the handling and injection of Anakinra.

Patients receiving Anakinra may experience a decrease in neutrophil counts. In the placebocontrolled studies, 8% of patients receiving Anakinra had decreases in neutrophil counts of at least 1 World Health Organization (WHO) toxicity grade compared with 2% in the placebo control group. Nine Anakinra-treated patients (0.4%) experienced neutropenia (ANC (Absolute Neutrophil Count) <1 × 109/L). For this reason, neutrophil counts will be monitored every thirty days while receiving Anakinra therapy. Therapy will be discontinued for any patient that develops moderate neutropenia (ANC<1000) (see section 9.5 Stopping Rules).

Renal insufficiency can reduce clearance of Anakinra. The mean plasma clearance of Anakinra in subjects with mild (creatinine clearance 50-80 mL/min) and moderate (creatinine clearance 30-49 mL/min) renal insufficiency was reduced by 16% and 50%, respectively. In severe renal insufficiency and end stage renal disease (creatinine clearance < 30 mL/min), mean plasma clearance declined by 70% and 75%, respectively. Less than 2.5% of the administered dose of Anakinra was removed by hemodialysis or continuous ambulatory peritoneal dialysis. For this reason, creatinine levels will be measured before and during therapy. Patients with a creatinine clearance of less than 49mL/min will not be eligible for this study. (Creatinine clearance will be measured by the following formula: [[140-age(yr)]*weight(kg)]/[72*serum Cr(mg/dL)](*0.85 for women). Patients that develop renal insufficiency while undergoing therapy (creatinine clearance of less than 49mL/min) will be prevented from continuing therapy (see section 9.5 Stopping Rules).

A 3.6 fold increase in the rate of lymphoma (a malignancy of the blood) was seen (0.12cases/100 patient years) in response to Anakinra (Patient years is the number of patients studied multiplied by the number of years studied). Patients with a history of a malignancy in the past 3 years may not be recruited for this study (see section 4.2 Exclusion Criteria).

2 Study Objectives

The purpose of this study is to determine if anakinra therapy may be an alternate therapy in patients with steroid resistant Autoimmune Inner Ear Disease.

Primary Objective

To assess the potential efficacy of anakinra in improving hearing thresholds in corticosteroidresistant patients with Autoimmune Inner Ear Disease.

Secondary Objective

To assess the safety and tolerability of a three month course of anakinra in corticosteroid resistant patients with Autoimmune Inner Ear Disease.

Tertiary Objective

To determine if measurement of circulating or induced IL-1 β expression, either prior to, during, or upon completion of therapy is predictive of clinical hearing recovery.

CONFIDENTIAL

This material is the property of the Feinstein Institute for Medical Research, North-Shore-LIJ Health System. Do not disclose or use except as authorized in writing by the study sponsor

3 Study Design

[figure not shown]
3.1 General Design

- The proposed study will be a Phase I/II, single-centered, open-label trial of Anakinra in corticosteroid resistant patients with AIED.
- Trial design:

Patient & Audiometric Criteria: All patients to be included in this phase I/II clinical trial must exhibit development of sensorineural hearing loss (SNHL) of greater than 30dB at one or more frequencies in *both* ears with evidence of active deterioration (elevated threshold) in at least one ear of 15 dB at one frequency (excluding 250 or 8kHz as a sole indicator), or 10dB at 2+ frequencies developing in >3 days but <90 days (7). If after the first 10 subjects are recruited, no untoward effect on hearing is identified, subjects with unilateral hearing loss may also be included. To utilize the expanded criteria defined above, progressive sensorineural hearing loss potentially attributed to anakinra therapy cannot be observed in the first 10 evaluable patients. If progressive SNHL is observed in over 25% but less than 50% of patients receiving anakinra during the initial phase, we would NOT utilize the expanded criteria.

- This group of potential patients may include those patients previously diagnosed as sudden SNHL if they demonstrated features suspicious for of autoimmune disease (if they have a systemic autoimmune disorder, family history of autoimmune disease, or if they had previous episodes of sudden sensorineural hearing loss in the same or contralateral ear), as long as they meet the audiologic criteria defined above with the exception that the hearing loss may evolve in less than 3 days. Similarly, patients previously diagnosed as Meniere's Disease with autoimmune features may be included if they meet the audiologic criteria as defined above. Patients were excluded from study if they had evidence of retrocochlear pathology on their MRI scan.
- **Definition of corticosteroid non-responder**: All patients must have been treated with 60mg of oral prednisone for a minimum of 7 days with a variable taper thereafter, for a minimum of 30 days in total, and response to prednisone therapy measured by audiometry before treatment and at approximately 30 days post-treatment. Audiometry will consist of a pure tone average ((PTA): here to include 250, 500, 1000, 2000, and 4000Hz) and speech discrimination score to be recorded pre and post treatment. Clinical responsiveness will be defined as either an average of 5 decibel or greater PTA improvement (as the average of five frequencies was recorded) in their post-treatment audiogram, or a greater than 12% improvement in the speech discrimination scores. In the event a patient with a pre-treatment profound SNHL demonstrates an improvement on PTA, however, no improvement in speech discrimination is noted, and the initial speech discrimination is 0%, this patient would be classified as a non-responder. Patients that received concurrent or sequential intratympanic corticosteroids may be included only if they received the 30 days of oral steroids as well.
- *Entrance into the research protocol:* Patients that failed to respond to corticosteroid therapy will be offered anakinra therapy as an alternate therapy to continued corticosteroid therapy. Given that anakinra is a daily subcutaneous injectable, it is unethical to perform a placebo controlled trial where a patient potentially could receive 84 consecutive days of injectable saline. Moreover, the total projected number of patients for this phase I/II trial is too low to consider a cross-over design. Thus an open-label trial design is proposed. Patients will be monitored every 28 days while on therapy

by audiogram and laboratory values. Laboratory values include a Complete Blood Count (CBC) with differential, SMA-7, HCG or UCG (for child-bearing aged females) and plasma IL-1 β levels/stimulation studies. Patients will complete daily logs as to injection site reactions and other potential side effects.

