4.1 Inclusion Criteria

1. Patients must have Autoimmune Inner Ear Disease, Meniere's Disease, or Sudden Sensorineural Hearing Loss with autoimmune features.

CONFIDENTIAL This material is the property of the Feinstein Institute for Medical Research, North-Shore-LIJ Health System. Do not disclose or use except as authorized in writing by the study sponsor

- 2. Age and Gender: males and females ages 13 to 75 weighing 90 lbs or greater will be recruited.
- 3. Patients must be capable of understanding and giving informed consent.
- 4. If the recruited patient is between the ages of 13 and 17, an assent will be obtained from the patient and consent from one parent/legal guardian prior to enrollment.
- 5. Patients must have SNHL of greater than 30dB at one or more frequencies in one or both ears with evidence of active deterioration (elevated threshold) in at least one ear of 15 dB at one frequency (excluding 250 or 8kHz as a sole indicator) on their audiogram, or 10dB at 2+ frequencies developing in >3 days but <90 days, or in the case of SSNHL, the hearing loss may evolve in less than 3 days if the patient displays features suggestive of an autoimmune disorder.
- 6. Patients must have previously undergone a trial of high-dose corticosteroid therapy, at 60 mg daily for a minimum of seven days, with a variable taper thereafter that consists of a total of 30 consecutive days of corticosteroid use. Patients must have demonstrated less than or equal to a 5 decibel average improvement in their PTA in response to corticosteroids as measured by their audiogram.
- 7. Patients may have a concurrent other autoimmune disease(s).

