7.1 Sample Size Determination & Statistical Methods

Corticosteroid resistant AIED patients currently have no therapeutic alternatives available to them. These patients that failed initial corticosteroid therapy are not expected to demonstrate a placebo effect, as they have already undergone 2 serial audiograms that demonstrated a <5dB PTA improvement in hearing for trial inclusion. A Simon 2-stage "optimal" design will be used to test the null hypothesis that the true objective response rate (RR) is 10% or less (which would not be clinically meaningful) versus the alternative hypothesis that the true response rate is 30% or greater. With a significance level of 0.05 and a power of 0.80, a maximum total of 29 evaluable patients will be required to assess the objective response rate. Ten (10) evaluable patients will be enrolled in Stage 1(R21 phase). If 1 or fewer objective responses are observed in the first 10 evaluable patients, then the trial will be terminated (do not proceed to R33). Primary milestone: If 2 or more objective responses (improvement in the PTA \geq 5dB) are observed in the first 10 patients (20%), we will proceed to the R33 phase.

If the RR is 10% or less, then the expected sample size for the trial is 15 patients and the probability of early termination at the end of the R21 phase (stage 1) is 74%. Overall, a total of approximately 38 patients may be enrolled in this R21/R33 study to ensure that the specified numbers of evaluable patients are available for analysis at each stage.

Given that anakinra may cause injection site reactions, it is possible that some patients will prematurely self-terminate the study. In order to appropriately evaluate the results, 29 patients would need to complete the 84-day course of anakinra. Overall, a total of 38 patients may be enrolled in this study to ensure that the specified numbers of evaluable patients are available for analysis at each stage.

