7.2 Subject Population(s) for Analysis

All-Treated Population: The analysis will be performed on all corticosteroid non-responders subsequently treated with 84 consecutive days of anakinra. The primary analysis will consist of determining whether an improvement in either audiometric threshold or speech discrimination can be achieved with anakinra in patients that did not respond to corticosteroids. The secondary analysis will be to determine whether anakinra can be administered safely for an 84 consecutive day period without significant complications in this patient population.

8 Safety and Adverse Events

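### Inclusion criterion 5 admits one-ear hearing loss without the safety look that section 3.1 requires first, and section 3.1 words that look in three inconsistent ways

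*Protocol*

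**What the plan says.** **Who may enter.** Section 3.1 sets an entry condition for all patients: sensorineural hearing loss "greater than 30dB at one or more frequencies in *both* ears", with active deterioration in at least one. Inclusion criterion 5 in section 4.1 reads differently: "Patients must have SNHL of greater than 30dB at one or more frequencies in one or both ears". It does not mention the first 10 patients or the decision in 3.1.

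**When unilateral patients may be added.** Section 3.1 gives three consecutive sentences, labelled here A, B and C.

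- A: "If after the first 10 subjects are recruited, no untoward effect on hearing is identified, subjects with unilateral hearing loss may also be included".
- B: to use the wider criteria, "progressive sensorineural hearing loss potentially attributed to anakinra therapy cannot be observed in the first 10 evaluable patients".
- C: "If progressive SNHL is observed in over 25% but less than 50% of patients receiving anakinra during the initial phase", the wider criteria would not be used.

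**Related text.** Section 7.1 enrols ten evaluable patients in Stage 1 and comes nearest to saying what evaluable means: "In order to appropriately evaluate the results, 29 patients would need to complete the 84-day course of anakinra". Section 7.2 describes its population as "all corticosteroid non-responders subsequently treated with 84 consecutive days of anakinra". Section 4.4.1 lists a pure tone average worsening of more than 20 dB in either ear as a reason to end treatment early. Section 4.4.2 keeps the data of withdrawn patients for analysis, above all for safety.

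**The concern.** Two things conflict. First, eligibility depends on which section is read. Section 4.3 offers enrolment to patients who meet the inclusion and exclusion criteria. Section 6 likewise sends patients to consent on those criteria (stated for the sponsor-investigator's own practice). The list in section 4 is therefore the working document, and it carries no trace of the restriction. The case is a realistic one: criterion 1 admits sudden hearing loss with autoimmune features, and section 1.1 describes sudden hearing loss as usually one-sided.

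Second, the condition for adding unilateral patients has no single meaning. A and B tolerate no event, while C names a percentage band that would be unnecessary if A and B governed. The three sentences also differ in whom they count and in whether the loss must be attributed to the drug.

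At stake are a clear hearing-safety decision before the population is widened (worsening hearing is a named safety endpoint in section 3.3) and certainty about who belongs in Stage 1, on which the milestone of 2 responses in 10 rests.

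**Working it through.** **1. The plan's own figures.** The protocol gives no operating figure for the expansion rule. Its Simon design (section 7.1: null 10%, alternative 30%, stop at 1 or fewer of 10, maximum 29) reproduces:

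- Probability of early termination at 10% = P(X ≤ 1), X ~ Binomial(10, 0.10) = 0.349 + 0.387 = 0.736 (stated 74%).
- Expected size = 10 + (1 − 0.736) × 19 = 15.0 (stated 15).
- An exact search returns the same stage sizes, with a final cut-off of 5 of 29 (reject above it), significance level 0.047 and power 0.805.

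The sample size is not in question.

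**2. Eligibility side by side.** Take a patient with qualifying loss in one ear, screened before the look. Section 3.1 says not eligible; criterion 5 says eligible. Nothing in either passage says which prevails.

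**3. The three gate sentences on 10 patients.** 25% of 10 is 2.5 and 50% is 5, so C covers exactly 3 or 4 events.

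| Events in 10 | A and B | C |
|---|---|---|
| 0 | expansion allowed | not named |
| 1–2 | barred | not named; tolerated by implication |
| 3–4 | barred | barred |
| 5 or more | barred | not named |

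The table treats every event as one that A and B would count. If C has a function of its own, the readings part at 1 or 2 events.

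**4. How often that zone is reached.** The protocol gives no rate of progressive loss, so the rate p is an assumption. With X ~ Binomial(10, p), P(1 or 2) = 10p(1−p)⁹ + 45p²(1−p)⁸.

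- p = 0.05: 0.315 + 0.075 = 0.390
- p = 0.10: 0.387 + 0.194 = 0.581
- p = 0.20: 0.268 + 0.302 = 0.570

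The chance that expansion opens is P(0) under zero tolerance, and P(0) + P(1) + P(2) if up to 2 events are tolerated.

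| p | Zero tolerance | Up to 2 tolerated | Difference = P(1 or 2) |
|---|---|---|---|
| 0.05 | 0.599 | 0.988 | 0.39 |
| 0.10 | 0.349 | 0.930 | 0.58 |
| 0.20 | 0.107 | 0.678 | 0.57 |

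**5. The denominators.** A counts subjects recruited, B evaluable patients, and C patients receiving anakinra. Section 7.1 allows 38 enrolled for 29 evaluable. At that ratio, 10 evaluable patients need 10 × 38/29 = 13.1, so 13 or 14 enrolled. Three events are then 3/10 = 30% (inside C's band) or 3/13 = 23% (outside it), depending on the denominator.

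A has a timing problem as well. When the tenth subject is recruited, that subject has no on-treatment audiogram, since section 5.3 schedules the first at day 28.

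**6. If evaluable means completers.** Suppose ten patients complete without an event and k others are withdrawn under 4.4.1 for more than 20 dB worsening. B then reads 0 of 10, while the rate among treated patients is k/(10 + k): 1/11 = 9%, 2/12 = 17%, 3/13 = 23%.

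**7. Attribution and definition.** Only B requires that the loss be potentially attributed to anakinra. A refers to any untoward effect on hearing, C to any progressive loss. None of the three says how large a change counts as progressive. Section 3.1's entry definition of deterioration and 4.4.1's withdrawal limit are both available, but neither is linked to the gate.

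**The case against.** The best defence is that the text can be harmonised. Criterion 5 may describe the whole-trial population, with 3.1 restricting the first 10. C never permits expansion at 25% or below; it only names a range in which expansion would not occur. If A and B govern, every count has an answer. The trial is single-centre, so staff are likely to know section 3.1. Hearing is also protected by the withdrawal limit in 4.4.1 and 8.5 and by an independent board that sees audiometric data every six months (8.6.1).

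Much of this stands, and it limits the point. A reader might infer four stronger things that the document does not support.

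- *That the gate counts hearing loss only in completers, so the worst losses cannot enter it.* Only B uses the word evaluable, and its completer meaning is inferred from 7.1 and 7.2. A and C as worded reach withdrawn patients, 4.4.2 keeps their data, and completers with smaller losses still count under B.
- *That five or more events lead to no decision.* C does not name that range, but A and B already bar expansion there.
- *That adding unilateral patients breaks the Simon design's assumption of one response rate.* Nothing in the protocol shows that they respond differently, and expansion is a stated feature.
- *That unilateral patients are expressly admitted from the first patient.* Criterion 5 has no timing condition, which allows that reading but does not state it.

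The defence does not remove the missing condition in criterion 5, nor explain why C exists if A and B decide everything.

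**Conclusion.** The point holds as a contradiction between sections 3.1 and 4.1, together with an expansion rule that is not stated consistently. Criterion 5, followed as written, could enrol unilateral patients in Stage 1 against section 3.1. Sentence C is either redundant or implies a looser limit than A and B.

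On 10 patients the two readings differ at 1 or 2 events, with probability 39%, 58% or 57% at assumed rates of 5%, 10% or 20%. These figures assume independent patients, a denominator of 10 for all three sentences and the same event counted in each. They show how often the wording would matter if C is given independent force. They do not measure harm or error rates.

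The loss of withdrawn patients from the count applies to sentence B alone, and only if evaluable means 84-day completers. The Simon figures are correct. The wording should be corrected, but the defect does not invalidate the design.

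**What to change.** Reconcile sections 3.1 and 4.1 by making one-ear entry in criterion 5 conditional on the decision in 3.1, with a cross-reference.

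Replace the three gate sentences with one rule that has:

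- an action for every possible count: 0 to 10 if the look is at the first 10 dosed, or up to the number dosed if it waits for ten evaluable patients;
- one definition of progressive loss and one attribution standard;
- one denominator, all dosed patients including those withdrawn;
- a stated time for the look, so that each patient counted has on-treatment audiometry or a withdrawal audiogram.

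Define evaluable where it is first used. The threshold is for the sponsor and the DSMB to set; none is proposed here.

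The cost is a protocol wording amendment with no change to the sample size. The small downside is that unilateral enrolment may open slightly later.

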4.3 Subject Recruitment and Screening

Subjects will be recruited from the practices of several Neurotologists and Otolaryngologists from the North Shore-LIJ Health System. No recruitment materials will be disseminated; however, patients within these practices with a diagnosis of AIED, SSNHL or Meniere's Disease may be sent letters informing them of this clinical trial. All patients that are treated with corticosteroids (60mg per day for 7 days with a taper thereafter to 30 days of treatment in total) will be informed of the study availability to them only if they fail to respond to corticosteroids as measured on the audiogram at approximate 30 day post-treatment interval. The study will be described to the patient. Pre-treatment laboratory tests will be performed for inclusion (CBC, SMA-7, beta HCG or UCG (if female of child-bearing age)) at visit 1 (or within 2 weeks prior). Plasma IL-1 β and in vitro expression of IL-1 β in PBMC and monocytes will also be measured. Patients that fail corticosteroid therapy and meet inclusion and exclusion criteria will be given the option of enrolling in this phase I/II trial and receiving Anakinra. Alternatively, they may opt to receive continued corticosteroids, or no further treatment. It is possible that a number of patients will not wish to perform daily injections for 84 days.

Some patients that failed corticosteroid therapy (as measured by a pre and post treatment audiogram) may be referred by non-study physicians for participation in this study. Inclusion of these patients may be considered if no greater than 30 days has elapsed since the discontinuation of corticosteroids, and that the patient received 30 days of prednisone. In the event the patient did not receive 30 days of prednisone, the patient will be treated again with 60mg of prednisone for 7 days and a variable taper to achieve 30 days of continuous therapy. Audiometry will be repeated again at the end of the treatment. If the patient is still a "non-responder", they will have the option to enroll in this study.

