6.1 Visit 1(Baseline)

Once the corticosteroid resistant patient has been identified at the end of a 28-30 day course of oral corticosteroids, enrolled patients will undergo blood testing (If the patient underwent a CBC, SMA-7 within 2 weeks prior to visit 1, those bloods will be accepted as enrollment criteria bloodwork). The audiogram taken at the end of the corticosteroid treatment will be used as the time 0 audiogram. Throughout the study, the audiologists will be blinded to the study treatment timepoint. Blood will be taken for a CBC, SMA-7, serum HCG or UCG (if female of childbearing age) and plasma IL-1 β and studies for IL-1 β stimulation in PBMC (30cc). The labs will be checked: if there is no evidence of neutropenia, renal insufficiency or pregnancy, the patient will be asked to meet with study nurses for instruction for self administration of anakinra. The patient will be asked to maintain a daily log of injections, injection site reactions and any associated symptoms (fluctuating hearing, vertigo, tinnitus, headaches).

6.2 Visit 2

At 28 days post-initial Anakinra treatment the patient will return for repeat audiometric testing and provide a blood sample (30cc). The daily logs would be reviewed by the study nurses weekly. The logs would be reviewed by the clinician at the time of the visit. Injection sites would be inspected and reactions documented. The blood specimen would be used to determine the CBC with differential, SMA-7, serum HCG (for females of child-bearing age) and IL-1 β plasma level and induction. The patient would be instructed to bring any remaining drug to the visit (if possible) as well as the spent syringes in the sharps container. The patient would be given a new 28 day supply of Anakinra and a new sharps container. CBC and SMA-7 results would be reviewed within 72 hours and any patients with changes in their white blood cell numbers, neutrophils numbers or creatinine values will be contacted. Any patient that develops neutropenia or renal insufficiency will be excluded from receiving further drug.

6.3 Visit 3

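### The protocol does not require an audiogram after the last intratympanic steroid dose, so a gain from an injection given after the time-0 audiogram can be counted as an anakinra response

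*Protocol*

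**What the plan says.** Section 3.1 of the protocol sets one condition for patients who had intratympanic steroid: "Patients that received concurrent or sequential intratympanic corticosteroids may be included only if they received the 30 days of oral steroids as well". The same section defines a non-responder by audiometry before prednisone and about 30 days later. Section 4.1, item 6, likewise describes an oral-type course and the change in pure tone average (PTA) that followed corticosteroids.

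Section 6.1 describes the resistant patient as "identified at the end of a 28-30 day course of oral corticosteroids". It then takes as time 0 the audiogram made when corticosteroid treatment ends, without naming a route. Section 5.3 lists audiometry at day 0 as well as days 28, 56 and 84.

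For patients referred by non-study physicians, section 4.3 allows entry if "no greater than 30 days has elapsed since the discontinuation of corticosteroids". It orders repeat audiometry only when the patient had not completed 30 days of prednisone.

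The endpoint in section 3.2 compares hearing with the threshold before anakinra. Section 7.1 counts a PTA gain of at least 5 dB as an objective response.

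**The concern.** Section 7.1 expects no placebo effect because two serial audiograms have already shown less than 5 dB of improvement. That argument needs the second audiogram to come after all steroid exposure. It fails for a patient who completes prednisone, has the end-of-course audiogram, and is then given intratympanic steroid before anakinra starts. Any gain from the injection would fall between time 0 and day 84.

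The PTA cut-off for an anakinra response is the same 5 dB that defines a steroid response, so nothing in the scoring separates the two. With one arm and a 10% null rate, each such gain adds directly to the responder count, and the error runs only in favour of the drug. Stage 1 is the sensitive point: 2 responses in 10 patients are enough to continue, so one misattributed response can decide it.

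**Working it through.** **Can the sequence occur under the text?**

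1. Sequential intratympanic steroid is allowed, and the completed oral course is the only condition (3.1).
2. Resistance is established at the end of the oral course (6.1). If the end of corticosteroid treatment in the next sentence means that course, time 0 is fixed there too.
3. A referred patient may enter up to 30 days after corticosteroids stop. With 30 days of prednisone completed, no repeat audiogram is triggered (4.3).
4. No section asks for an audiogram after the last injection.

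The sequence is therefore permitted on one natural reading, though not on every reading.

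**The plan's own design figures (7.1)**

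Inputs:
- Null: "the true objective response rate (RR) is 10% or less".
- Alternative: "the alternative hypothesis that the true response rate is 30% or greater".
- Size: "With a significance level of 0.05 and a power of 0.80, a maximum total of 29 evaluable patients will be required".
- Stage 1 rule: "If 1 or fewer objective responses are observed in the first 10 evaluable patients, then the trial will be terminated".
- Under the null, the section states "the expected sample size for the trial is 15 patients and the probability of early termination" at stage 1 of 74%.

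Check:
- P(stop at stage 1) = 0.9^10 + 10 × 0.1 × 0.9^9 = 0.3487 + 0.3874 = 0.736.
- Expected N = 10 + (1 − 0.7361) × 19 = 15.01.
- A search for the smallest expected N with alpha ≤ 0.05 and power ≥ 0.80 returns 1/10 then 5/29, with exact alpha 0.0471 and power 0.8051.

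The stated figures reproduce. The final cut-off (success with 6 or more of 29) is not printed in the protocol; it is inferred from this match.

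**Sensitivity to misattributed gains**

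Let f be the share of evaluable patients injected after the time-0 audiogram, and q the share of those who gain at least 5 dB from the injection. Both are assumptions. Anakinra's true rate is held at the 10% null, and the two kinds of gain are taken as independent. Then:

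- Apparent rate p = 0.10 + 0.90 × f × q.
- P(success) = sum over x = 2 to 10 of P(X1 = x) × P(X2 ≥ 6 − x), with X1 ~ Bin(10, p) and X2 ~ Bin(19, p).
- P(pass stage 1) = 1 − P(X1 ≤ 1).
- Extra responses expected if all 29 are studied = 29 × 0.90 × f × q.

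| f | q | Apparent rate | Extra responses in 29 | P(pass stage 1) | P(false success) |
|---|---|---|---|---|---|
| 0 | – | 0.100 | 0 | 0.264 | 0.047 |
| 5% | 10% | 0.1045 | 0.13 | 0.281 | 0.056 |
| 10% | 20% | 0.118 | 0.52 | 0.334 | 0.089 |
| 20% | 20% | 0.136 | 1.04 | 0.403 | 0.147 |
| 30% | 30% | 0.181 | 2.35 | 0.564 | 0.341 |

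The Study Summary speaks of a response rate of 30% or more to move on. Read as an observed threshold, that would need 9 of 29 (0.30 × 29 = 8.7). The last column would then be lower throughout, and the stage 1 column unchanged.

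**The case against.** The strongest reply is that the text already allows a later baseline. The time-0 sentence in 6.1 speaks of corticosteroid treatment, not the oral course, so for a patient with sequential injections it can mean the audiogram after the last one. Section 5.3 lists a day-0 audiogram for every enrolled patient, and 3.2 compares with the threshold before anakinra. If the audiogram about 30 days post-treatment in 3.1 and 4.3 is counted from the end of prednisone, injections in that interval would also precede it.

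This shows that the text is ambiguous, not that the gap is closed. The sentence in 6.1 just before the time-0 rule names the oral course, 3.1 ties non-response to prednisone, and 6.1 reuses an existing audiogram instead of the one listed in 5.3.

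Some stronger conclusions that a reader might draw do not stand:

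- **That every intratympanic patient biases the result.** Concurrent or earlier injections come before the time-0 audiogram. Only later injections matter, and only with a gain of at least 5 dB.
- **That these patients fall outside the study population.** They meet the protocol's own definition, which rests on failed prednisone and expressly admits intratympanic treatment.
- **That each injection restarts the 30-day window in 4.3.** This requires the term corticosteroids to include injections. The same meaning in 6.1 would move time 0 past the last injection and remove the problem.
- **That the false-positive rate is about one in three.** That is the top of an assumed range. If few patients are affected, the change is close to nothing.

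**Conclusion.** The point holds as a gap in the definition of baseline. On a natural reading of 3.1 and 6.1, a patient injected after the time-0 audiogram can contribute a steroid gain to the anakinra response count, and no section prevents it. The bias can only favour the drug.

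Its size cannot be derived from the documents. Under the assumed inputs, the false-positive probability ranges from 0.056, barely above the nominal 0.047, to 0.341; it is 0.089 with 10% of patients affected and 20% of them gaining. These values rest on the inferred 5/29 cut-off, a true anakinra rate of 10%, and independence of the two effects. The stated sample size, expected N and early-termination figures are correct.

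It should be corrected in the protocol, because later analysis cannot supply a baseline audiogram that was never taken.

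**What to change.** Reconcile sections 3.1, 4.1 (item 6), 5.3 and 6.1 so that one audiogram both confirms non-response and serves as time 0, taken after the last pre-study corticosteroid dose by any route and before the first anakinra dose. The day-0 audiogram in 5.3 can serve, provided 6.1 no longer points to a different one. Record the date of the last intratympanic dose; section 5.6 already collects therapies from the previous three months.

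A repeat of the primary response rate without patients who had sequential injections is optional and may sit in the SAP.

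The cost is protocol wording, plus a repeat routine audiogram and a short delay to entry for the few patients concerned. Some of them may prove to be responders at that audiogram and so not qualify. The sample size and the Simon design do not change.
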